7.4.1.2 Methods of Recording and Assessing Adverse Events

At each trial visit, the subject will be queried on changes in his/her condition. During the reporting period of the trial any unfavorable changes in the subject's condition will be recorded as AEs, whether reported by the subject or observed by the investigator.

Complete, accurate and consistent data on all AEs experienced for the duration of the reporting period (defined below) will be reported on an ongoing basis in the appropriate section of the CRF. Among these AEs, all SAEs and all nonserious AEs of special interest must be additionally documented and reported using the appropriate Report Form as described in Section 7.4.1.4.

It is important that each AE report include a description of the event, its duration (onset and resolution dates and times to be completed when it is important to assess the time of AE onset relative to the recorded treatment administration time), its severity, its causal relationship with the trial treatment, any other potential causal factors, any treatment given or other action taken (including dose modification or discontinuation of the IMP) and its outcome. In addition, serious cases should be identified and the appropriate seriousness criteria documented.

Specific guidance can be found in the CRF Completion and Monitoring Conventions.

7.4.1.3 Definition of the Adverse Event Reporting Period

The AE reporting period for safety surveillance begins when the subject is included into the trial (date of first signature of informed consent) and continues through the trial's End-of-Treatment visit, 28 days after last trial drug administration. After the End-of-Treatment visit only treatment-related AEs have to be documented through the post-treatment safety follow-up period, defined as 10 weeks after the last trial drug administration.

Any SAE suspected to be related to the trial treatment must be reported whenever it occurs, irrespective of the time elapsed since the last administration.

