	
treatment related AEs have to be documented until the post-treatment safety follow-up visit. Subjects with a serious AE ongoing at the post-treatment safety follow-up must be monitored and followed up by the investigator until stabilization or until the outcome is known, unless the subject is documented as “lost to follow-up”.
 
Subjects without progressive disease at the end-of-treatment visit will be followed up for disease progression (CT / MRI scans every 12 weeks) up to 1 year. In addition, subjects will be followed for any AE suspected to be related to trial treatment, especially for the occurrence of new autoimmune events up to 3 months after the last dose of avelumab.
 
After the end-of-treatment visit, subjects will be followed quarterly for survival (including assessment of any further tumor therapy). The survival follow-up will continue until 1 year after the last subject receives the last dose of avelumab.

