As one can deduce from the clinical experience with ipilimumab, which blocks cytotoxic T lymphocyte antigen-4 (CTLA-4), a negative regulator of T-cell activation like PD-L1, potential side effects of PD-L1 antagonism include immune-related adverse reactions, which can be severe and may involve the gastrointestinal, liver, skin, endocrine, or other organ systems (57-61). Skin-related AEs can be expected after 2 to 3 weeks, gastrointestinal and hepatic AEs after 6 to 7 weeks, and endocrinologic AEs only after an average of 9 weeks (62) and constitute the clinically most relevant safety concern apart from acute severe infusion reactions. The kinetics of the occurrence of such irAEs have not been reported for either BMS-936559 targeting PD-L1 (5) nor for the anti-PD-1 monoclonal antibody BMS-936558 (6). However, their toxic effects seem to be less common and of lower grade compared with ipilimumab. Nevertheless, careful monitoring of such AEs of special interest (AESI) is implemented in this protocol throughout the complete treatment period and up to 3 months post-treatment for follow-up (see Sections 7.1.4 and 7.4.1.1).

A direct benefit is considered unlikely for participants in this Phase I trial, at least in the low doses of the dose escalation part. However, durable partial responses have been reported with another anti-PD-L1 monoclonal antibody (6). Therefore, only subjects with malignancies for which no standard therapy exists or subjects having experienced a failure of standard therapy are eligible for this part of the study (i.e., 1 and 3 mg/kg). However, allometric scaled human simulations suggests that the proposed initial dose of 1.0 mg/kg is expected to result in at least 50% target occupancy, which may be sufficient to induce beneficial clinical effects. Moreover, expansion on a dose level displaying pharmacological and/or clinical activity, to enrich for subjects in selected indications will be done.

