5.1.6 Planned Treatment Duration

The trial duration for a subject is estimated to be up to 30 weeks. This includes an 18-day screening period (decision will be made in this period for subjects’ trial inclusion if all eligibility criteria are met), a treatment duration until confirmed progression, unacceptable toxicity, or any criterion for withdrawal from the trial or IMP occurs (see Section 5.5) and an end-of-treatment visit 4 weeks after the last dose of avelumab administration.

For subjects who achieve a CR on avelumab therapy and then subsequently develop disease progression after stopping therapy, but prior to the end of the trial, one re-initiation of treatment at the same dose and schedule is allowed at the discretion of the investigator and agreement of the trial Medical Monitor. In order to be eligible for retreatment, the subject must not have experienced any toxicity that led to treatment discontinuation of the initial avelumab therapy. Prior to re-initiation of the study treatment, malignant disease needs to be radiologically re-staged to assess all known sites of the disease and to establish a new baseline for subsequent tumor measurements. Relevant safety laboratory results must be available and verified prior to re-initiating of treatment. Subjects who re-initiate treatment will stay on study and will be treated and monitored according to the protocol and the “until progression” schedule in the Schedule of Assessments (see [Appendix D](#)).

Moreover, any ADRs should be followed until they resolve, return to baseline, or are irreversible (see Section 7.1.4 for details).

Planned first subject in: Q1, 2013.

Planned date last subject out (dose escalation): Q2, 2018.

Planned date last subject out (after expansion and follow-up): Q2, 2019.

In the case of study termination (see Section 5.6), subjects continuing to benefit from study treatment may still have access to study treatment via enrollment in a rollover study if not available through some other mechanism (eg, expanded access, marketed product).

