7.1.4 Post-Treatment Safety Follow-Up

All subjects will have a subsequent visit scheduled 10 weeks after the last administration of avelumab. The visit will include the following full assessment of safety parameters (refer to [Appendix I](#)):

- Any treatment related AEs and concomitant medications will be documented, including further anti-cancer therapy.
- Vital signs and body weight will be measured.
- Physical examination will be performed.
- ECOG performance status will be assessed.
- 12-lead ECG will be assessed.
- Laboratory testing consisting of the following will be assessed:
 - hematology, hemostaseology, full serum chemistry, and full urinalysis
 - T4 and TSH levels
 - PK sample (any remaining sample may be used for ADA determination)
- A urine β -HCG pregnancy test (in women of child bearing potential) will be conducted.

After the End-of-Treatment visit only treatment-related AEs have to be documented until the Post-treatment Safety Follow-up visit. Subjects with a SAE ongoing at the post-treatment safety follow-up visit must be monitored and followed up by the investigator until stabilization or until the outcome is known, unless the subject is documented as “lost to follow up.”

Subjects without progressive disease according to RECIST 1.1 at the end-of-treatment visit will be followed up for radiographic disease progression (CT / MRI scans) every 12 weeks up to 1 year.

After the end-of-treatment visit, subjects will be followed quarterly (\pm 14 days) for survival (including assessment of any further tumor therapy). The survival follow-up will continue until 1 year after the last subject receives the last dose of avelumab.

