3. Subjects with an ADR ongoing at the end of the treatment visit and for any AE suspected to be related to trial treatment occurring up to 3 months after the last dose of avelumab will continue to be followed. Subjects without progressive disease at the end-of-treatment visit will be followed up for disease progression (CT / MRI scans every 12 weeks) up to 1 year or until disease progression, whichever is first. In addition, subjects will be followed quarterly (± 14 days) for survival (including assessment of any further tumor therapy). The survival follow-up will continue until 1 year after the last subject receives the last dose of avelumab. See Section 7.1.4 for details.
4. 12-lead ECG should be assessed before infusion and 2 hours (± 20 minutes) after infusion.
5. Core serum chemistry includes liver function panel (alkaline phosphatase, aspartate aminotransferase (AST), alanine aminotransferase (ALT), bilirubin), acute chemistry panel (sodium, potassium, chloride, blood urea nitrogen (BUN)/total urea, creatinine, glucose), and mineral panel (magnesium, phosphorus, calcium). If full and core chemistry are scheduled at the same visit, the full chemistry will be performed.
6. Full chemistry panel and other laboratory studies are detailed in Table 7.2. Serum electrophoresis only at end-of-treatment.

7. Full urinalysis at Week 1/Day 1 and end-of-treatment and basic urinalysis (protein content only) at each visit as indicated prior to administration of study drug. If urinalysis (full or basic) is positive for protein (dipstick), sediment will be evaluated. Urinalysis does not have to be performed in subjects with urothelial cancers.
8. Results of the most recent pregnancy test (urine β -HCG) should be available prior to next dosing of IMP.
9. In general, the tumor visit time window is 5 days prior to dosing. In case a tumor response according to RECIST 1.1 is documented during the course of the study confirmation of the response should be performed according to RECIST 1.1 after 6 weeks. CT scan or MRI (if MRI is used, CT of chest is mandatory) should always be used.
10. Brain CT/MRI scan should be done if clinically indicated by development of new specific symptoms.
11. A bone scan should be done as clinically indicated. Bone metastases that had been detected at screening need to be followed at the tumor evaluation visits.

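### The protocol holds two incompatible post-treatment safety rules (3 months and every ADR to resolution, against 10 weeks and SAEs only), so non-serious related events after day 70 and late outcomes need not be collected

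*Protocol*

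**What the plan says.** **The longer rule.** The synopsis has subjects followed for any AE suspected to be related, "especially for the occurrence of new autoimmune events up to 3 months after the last dose of avelumab". Both SAPs repeat this in their trial summaries. Section 3.7 (benefit and risk) says monitoring of events of special interest runs "up to 3 months post-treatment for follow-up (see Sections 7.1.4 and 7.4.1.1"). Section 5.1.6 adds that "any ADRs should be followed until they resolve, return to baseline, or are irreversible (see Section 7.1.4 for details"). In the retreatment schedule of Appendix I, footnote 3 continues follow-up of ADRs ongoing at the end of treatment and "for any AE suspected to be related to trial treatment occurring up to 3 months after the last dose of avelumab".

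**The shorter rule.** Section 7.1.4 states: "All subjects will have a subsequent visit scheduled 10 weeks after the last administration of avelumab". It goes on: "After the End-of-Treatment visit only treatment-related AEs have to be documented until the Post-treatment Safety Follow-up visit". Section 7.4.1.3 sets the same limit: "through the post-treatment safety follow-up period, defined as 10 weeks after the last trial drug administration". Beyond that visit, Section 7.1.4 continues follow-up for one group only: "Subjects with a SAE ongoing at the post-treatment safety follow-up visit must be monitored and followed up by the investigator until stabilization". Section 7.4.1.6 repeats both limits, as do Appendix I footnote 18 (dose escalation and expansion schedules) and footnote 16 (once-weekly cohort). Section 7.4.1.3 makes one exception: a related SAE is reported whenever it occurs.

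**The SAP.** Table 15 of the expansion SAP accepts an irAE with onset up to 90 days after the last dose. Section 17.1.5 plans a listing of irAEs that start or worsen after the on-treatment period.

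**The concern.** Sections 3.7 and 5.1.6 rely on Section 7.1.4 to carry out what they promise. Section 7.1.4 has no 3-month period and no rule for following a non-serious ADR. Section 7.4.1.1, also cited in 3.7, has no 3-month period either. A site that looks up the reporting period finds 10 weeks, and Section 7.4.1.2 ties CRF recording to that period. Retreated subjects come under the other rule, so two groups in the same trial are followed differently.

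Two kinds of data are at stake: late-onset non-serious related events, which the SAP's irAE definition and post-treatment listing expect to find, and the end date and outcome of non-serious related events that outlast the 10-week visit. Number, severity and duration of treatment-related AEs are secondary endpoints (Protocol Section 8.3.2).

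**Working it through.** No sample size, power or alpha depends on this point. The check sets the rules side by side and counts days.

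**1. The two rules**

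| Question | Synopsis, 3.7, 5.1.6, retreatment footnote 3 | 7.1.4, 7.4.1.3, 7.4.1.6, Appendix I footnotes 18/16 |
|---|---|---|
| New non-serious related AE | to 3 months after last dose | to the 10-week visit |
| Non-serious ADR still ongoing | to resolution, baseline or irreversibility (5.1.6) | no follow-up required after that visit |
| SAE ongoing at the 10-week visit | covered if it is an ADR | to stabilization or known outcome |
| New related SAE | covered to 3 months | reported whenever it occurs (7.4.1.3) |

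The rules differ for non-serious events only.

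**2. Length of the onset gap**
- Required documentation: 10 × 7 = 70 days.
- Three months at the SAP's 30.4375 days per month: 3 × 30.4375 = 91.3 days. Gap: 91.3 − 70 = 21.3 days; 21.3 / 91.3 = 23%.
- SAP Table 15: 90 − 70 = 20 days; 20 / 90 = 22%.

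**3. Which outputs are touched**
- Expansion SAP Section 11 ends the on-treatment period at last dose + 30 days at the latest. Section 17.1 restricts AE tables to TEAEs unless otherwise specified, and Section 17.1.5 summarizes treatment-emergent irAEs. Onsets after day 70 enter none of these counts.
- The listing of irAEs after the on-treatment period draws on data that are required only to day 70 for non-serious events, while Table 15 accepts onset to day 90.
- Table 15 also asks whether an event resolved spontaneously within 7 days. For onsets after day 63 (70 − 7), that answer may fall beyond the required follow-up.
- Duration: a TEAE with onset on day 30 and still open on day 70 has 70 − 30 + 1 = 41 days observed under the SAP's duration formula (stop − start + 1). Earlier onsets have more. Missing stop dates therefore affect only long-lasting non-serious events. The expansion SAP reports AE duration in the AE listing (Section 17.1.1).

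**4. Share of events that are non-serious**
Protocol Section 3.4 reports 69 potential irAEs, of which 56 were non-serious: 56 / 69 = 81%. It does not say how many began after treatment ended, so the number falling on days 71 to 90 cannot be estimated from the documents.

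**The case against.** The strongest reply is that the rules can be read together. The synopsis gives the 10-week rule and then adds the 3-month follow-up to it, and both SAPs carry the two together. On that reading 10 weeks is the minimum for documentation and 3 months is additional follow-up. Section 5.1.6 and the synopsis bind sites as much as Section 7.4.1.3 does, so what sites will actually do is a prediction.

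Other text narrows the gap. Related SAEs have no time limit. Section 7.4.3 has clinically significant new laboratory abnormalities repeated weekly until normal, chronic or stable, with no stated 10-week stop. Section 7.4.1.6 makes the investigator responsible for necessary follow-up procedures. In Appendix I the AE row is already marked in the 3-monthly follow-up column for dose escalation and expansion.

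Much of this stands. It limits the point to non-serious events and to what is not required, as opposed to what is forbidden or known to be missing. It does not remove the conflict: the cross-references still lead to a section without the promised rules, and the footnote attached to the marked AE row (18) repeats the 10-week limit.

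A reader might infer more than the documents support:
- **That irAEs ongoing at week 10 are lost.** They are already on the CRF with onset, grade and causality. Only the later course and outcome are not required.
- **That related-AE and irAE table counts are too low.** Those tables close by last dose + 30 days.
- **That the steroid tapers in Table 6.2 measure the loss.** The tapers apply only where steroids are given. For Grade 3–4 pneumonitis the table calls for hospitalization, which makes the event an SAE with continued follow-up.

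**Conclusion.** The inconsistency is real and more than clerical, because the SAP's irAE definition reaches beyond the window in which sites must document non-serious events. Onset need not be recorded for about 20 of the SAP's 90 days (22%), or about 21 of the 91 days in 3 months (23%). Stop date and outcome need not be collected for non-serious related AEs still open at week 10. The effect falls on the post-treatment irAE listing, on irAE case classification late in the 90-day window, and on the recorded duration of long-lasting non-serious events. Serious related events, TEAE incidence and treatment-emergent irAE incidence are unaffected.

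This rests on a site applying the reporting period as Section 7.4.1.3 defines it. The documents do not show how many events are involved. The correction should be made, but no primary result depends on it.

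**What to change.** Reconcile the synopsis, Sections 3.7, 5.1.6, 7.1.4, 7.4.1.3 and 7.4.1.6, and Appendix I (footnotes 18 and 16, and retreatment footnote 3) so that they state one documentation window for treatment-related AEs and one rule for following ongoing ADRs, applied alike to first-course and retreated subjects. Correct the cross-references in 3.7 and 5.1.6 so that they lead to that text. Make the collection window match the 90-day onset limit in Table 15 of the expansion SAP. If the shorter window is kept, change Table 15 and the 3-month statements to agree with it.

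If the window extends past 10 weeks, late onset and outcome can be asked for at the existing quarterly follow-up contact. Timing needs one check. Counted from an end-of-treatment visit at day 28, the first contact falls near day 119 (28 + 91), or days 105 to 133 with the ±14-day window. Counted from the last dose, it falls on days 77 to 105 (91 ± 14) and may come before day 90. The wording should therefore name the first contact on or after the end of the window.

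The cost is amendment wording and a related-AE question at a contact that already takes place; no visit is added. For subjects already past the window, the study report should state that non-serious onset after day 70 was not required to be recorded.

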7.4.1.4 Procedure for Reporting Serious Adverse Events / Adverse Events of Special Interest

Serious Adverse Events

In the event of any new SAE (of any Grade) occurring during the reporting period, the investigator must immediately (i.e., within a maximum 24 hours after becoming aware of the event) inform the Sponsor or designee by telephone, by fax or by e-mail.

When an event (or follow-up information) is reported by telephone, a written report must be sent immediately thereafter by fax or e-mail.

Reporting procedures and timelines are the same for any new information on a previously reported SAE (= follow-up).

For names, addresses, telephone and fax numbers for SAE reporting, see information included in the SAE Report Form.

All written reports should be transmitted using the SAE Report Form, which must be completed by the investigator following specific completion instructions. The AE section of the CRF must be completed. Relevant pages from the CRF may be provided in parallel (e.g., medical history, concomitant drugs).

In all cases, the information provided in the SAE Report Form must be consistent with the data on the event that is recorded in the corresponding sections of the CRF.

The investigator/reporter must respond to any request for follow-up information (e.g., additional information, outcome and final evaluation, specific records where needed) or to any question the Sponsor or designee may have on the AE within the same timelines as described for initial reports. This is necessary to permit a prompt assessment of the event by the Sponsor or designee and (as applicable) to allow the company to meet strict regulatory timelines associated with expedited safety reporting obligations.

Requests for follow-up will usually be made by the responsible Monitor, although in exceptional circumstances the Global Drug Safety department of the Sponsor may contact the investigator directly to obtain clarification or to discuss a particularly critical event.

Adverse Events of Special Interest

In the event of a non-serious immune-related reaction, the investigator must complete the AESI Report Form and send it to the Sponsor/designee immediately within 24 hours. Names, addresses, and telephone and fax numbers for AESI reporting will be included on the Report Form. Serious AESIs must be reported in an expedited manner as SAEs, as outlined above.

7.4.1.5 Safety Reporting to Health Authorities, Independent Ethics Committees/ Institutional Review Boards and Investigators

The Sponsor will send appropriate safety notifications to health authorities in accordance with applicable laws and regulations.

The investigator must comply with any applicable site-specific requirements related to the reporting of SAEs (and in particular deaths) involving his/her subjects to the IEC / IRB that approved the trial.

In accordance with ICH GCP guidelines, the Sponsor or designee will inform the investigator of “findings that could adversely affect the safety of subjects, impact the conduct of the trial, or alter the IEC’s/IRB’s approval/favorable opinion to continue the trial.” In particular and in line with respective regulations, the Sponsor or designee will inform the investigator of AEs that are both serious and unexpected and are considered to be related to the administered product (suspected unexpected serious adverse reactions [SUSARs]). The investigator should place copies of safety reports in the Investigator Site File. National regulations with regard to safety report notifications to investigators will be taken into account.

When specifically required by regulations and guidelines, the Sponsor or designee will provide appropriate Safety reports directly to the concerned health authority and lead IEC / IRB and will maintain records of these notifications. When direct reporting by the Sponsor or designee is not clearly defined by national or site-specific regulations, the investigator will be responsible for promptly notifying the concerned IEC / IRB of any safety reports provided by the Sponsor or designee and of filing copies of all related correspondence in the Investigator Site File.

For trials covered by the European Directive 2001/20/EC, the Sponsor’s responsibilities regarding the reporting of SAEs / SUSARs / Safety Issues will be carried out in accordance with that Directive and with the related detailed guidance.

